Participants will be divided into three groups: control, AFCO2L only and combined PDL and AFCO2L treatment. Both laser groups will receive 3 treatments 6 weeks apart. Outcome measures will be conducted before laser treatment, 6 weeks after the last treatment of laser and 3 months post laser treatment. This feasibility study will serve to inform a larger multi-centre RCT in terms of study power, outcome measure frequency and whether treatment streams can be refined.

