## 5. Methods

All adult patients treated at the Royal Victoria Infirmary Northern Regional Burn Centre will be screened for admission. Those patients who meet the selection criteria will be informed about the study and asked to participate at their six-week clinic appointment.

Each patient will be randomised to one of three groups: COMBINED LASER (CL), SINGLE LASER (SL) or CONTROL (C) group. A single hypertrophic scar site >1% -5% TBSA is required for each patient. This scar size is deemed appropriate for topical local anaesthesia laser treatment as an outpatient.

[figure not shown]
In the event that the patient has multiple or large areas of hypertrophic scar, study participation will only be offered if laser treatment under topical local anaesthesia is possible and if the study participant consents to this. If the study PI feels this is not feasible, study participation will not be offered and the patient will continue with standard of care as provided by the host unit.

The rationale for this is that it is unethical to treat an area of hypertrophic scar within a large scar burden as standard of care in our host institution would be to treat all areas with AFCO2L if deemed a suitable candidate. Furthermore, previous experience has illustrated that the subjective nature of PROMs makes it difficult for participants to provide meaningful answers if a small area of scar has been treated within a large scar volume; it is not possible to selectively comment on the daily physical/psychological impact of a small treated area if most of a limb/body is scarred.

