**Colorimetry** using a digital colorimeter will provide data on scar erythema and pigmentation. Both parameters will be measured at enrolment and study conclusion to assess whether combination laser alters scar redness and pigmentation versus standard care. Measurements are taken in triplicate from a region of interest in the study scar, allocated by the PI. Control colorimeter measurements are taken from the contralateral area if It is scar-free. If there is no contralateral area free of scar, an alternate site of unscarred skin may be used and documented.

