## 5.6 Sample size

Previous studies indicate a large effect size (Cohen's d 1.7). Therefore, for a size with 80% power and a 0.05 alpha, a sample size of 7 is required. We are proposing the conventional sample size of 30 patients for a feasibility study (10 participants per study arm). This will provide sufficient information to enable an accurate sample size calculation for use in a larger multicentre trial should a benefit be observed. If no benefit is seen to occur, then we can calculate the probability of having missed a potential benefit in our trial. This data will therefore inform the decision as to whether a future larger trial is warranted and necessary adjustments.

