# 7. Statistical methods

Descriptive, univariate statistics will be used to describe the general characteristics of the sample. Differences between "Control" and "Intervention" groups will be examined using the Wilcoxon Signed Rank test, and a p value < 0.05 will be considered to indicate statistical significance. All statistical analysis will be conducted using PRISM.

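### Section 7 names a paired rank test with no baseline covariate for three independent arms, although every outcome is measured at week 0; a baseline-adjusted comparison fits the design and is more precise at moderate correlation

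*Protocol*

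**What the plan says.** Section 5 sets a parallel design with one study scar per patient: "Each patient will be randomised to one of three groups". Section 5.6 plans 10 patients per arm.

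Section 1 says "Outcome measures will be conducted before laser treatment" and again afterwards. The visit tables in Section 5.4 show this for each arm: POSAS, MSS and BBSIP at week 0, month 4 and month 8. For colorimetry, Section 5.5 states that "Both parameters will be measured at enrolment and study conclusion".

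Section 7 is the whole analysis text. After descriptive statistics, it says that differences between one Control and one Intervention group "will be examined using the Wilcoxon Signed Rank test, and a p value < 0.05" is the criterion for significance. It does not name the variable tested (follow-up score or change), and it mentions no covariate, effect estimate or confidence interval. Section 5.3 describes random allocation by an online service and does not mention stratification.

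**The concern.** The signed-rank test works on pairs. Here the groups being compared consist of different patients, so there is no pair that spans two arms, and two group labels do not cover three arms. The sentence has to be rewritten in any case, which raises the question of what should replace it.

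The nearest replacement, a rank-sum test, has no place for the baseline score. With 10 patients per arm, baseline scar severity can differ noticeably between arms by chance, and part of that difference carries into an unadjusted contrast. Variation that the baseline score could explain also stays in the error term.

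The stake is what the trial can hand on. Section 5.6 wants the data to support an accurate sample size for a multicentre trial and a decision on whether one is warranted. A p-value from a rank test supplies neither an adjusted difference with its interval, nor the residual SD and correlation needed to size a baseline-adjusted main trial.

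**Working it through.** **1. The plan's own figure.** Section 5.6 takes Cohen's d = 1.7 and says "for a size with 80% power and a 0.05 alpha, a sample size of 7 is required". A two-sided two-sample t-test (noncentral t) gives n = 6.55, so 7 per arm (power 0.83 at 7, 0.76 at 6). A paired t-test would need 5. Two-sided and per arm are my readings, since the protocol states neither. The 7 therefore fits an unadjusted comparison of two independent groups, not the paired test in Section 7.

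**2. Precision.** Inputs: 10 per arm and three arms (Section 5.6); two-sided alpha 0.05; baseline/follow-up correlation ρ, **assumed**, because the protocol gives none. All differences are in units of the follow-up SD, with equal SDs at baseline and follow-up. The variance of a contrast between two arms is v × 2/10, where

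- unadjusted follow-up score, variance pooled over three arms: v = 1, 27 df
- change score: v = 2(1 − ρ), 27 df
- ANCOVA: v = (1 − ρ²) × (1 + 1/25), 26 df. The 1/25 is 1/(27 − 2), the expected cost of estimating a common slope.

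Solving for 80% power at v = 1 gives 1.30 SD. The other detectable differences are close to 1.30 × √v; for example, ANCOVA at ρ = 0.5 has v = 0.75 × 1.04 = 0.78, and 1.30 × √0.78 = 1.15.

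| Assumed ρ | v, ANCOVA | Detectable: unadjusted | Detectable: change | Detectable: ANCOVA | Power at 1.0 SD: unadjusted | Power at 1.0 SD: ANCOVA |
|---|---|---|---|---|---|---|
| 0.2 | 1.00 | 1.30 | 1.64 | 1.30 | 58% | 58% |
| 0.3 | 0.95 | 1.30 | 1.54 | 1.27 | 58% | 60% |
| 0.5 | 0.78 | 1.30 | 1.30 | 1.15 | 58% | 68% |
| 0.7 | 0.53 | 1.30 | 1.01 | 0.95 | 58% | 84% |

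Break-even with the unadjusted score is where (1 − ρ²) × 1.04 = 1, so ρ ≈ 0.2.

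If only the two arms of a contrast are used (18 df unadjusted, 17 df for ANCOVA with factor 1 + 1/16), the unadjusted 1.32 SD becomes 1.31 / 1.19 / 0.98 at ρ = 0.3 / 0.5 / 0.7. Power at 1.0 SD goes from 56% to 57% / 66% / 82%. At ρ = 0.2 ANCOVA is then slightly worse (1.34).

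**3. Chance imbalance.** For two given arms, the SD of the baseline mean difference is √(2/10) = 0.447. P(|gap| > 0.5 SD) = 2 × [1 − Φ(0.5/0.447)] = 2 × [1 − Φ(1.118)] = 0.26 on any one scale. A gap g shifts the expected follow-up contrast by ρg: for g = 0.5, by 0.15 / 0.25 / 0.35 SD at ρ = 0.3 / 0.5 / 0.7. It shifts a change-score contrast the other way by (1 − ρ)g: 0.35 / 0.25 / 0.15 SD.

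**4. Effect on error rates.** Simulation, 10 versus 10, normal scores, 3,000 runs per setting, no true effect, ρ = 0.3 / 0.5 / 0.7:

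- All runs: the rank-sum test rejects in about 4–5% on follow-up or change scores, and ANCOVA in about 5%.
- Runs with a baseline gap of at least 0.5 SD: 5.5 / 8.3 / 9.9% for follow-up scores, 7.9 / 9.5 / 6.7% for change scores, 4.0 / 5.8 / 5.0% for ANCOVA.

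At the protocol's own d = 1.7, power is about 0.93 for a rank-sum test on follow-up scores, and 0.96 / 0.98 / 0.998 for ANCOVA.

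**The case against.** A reader might infer that the plan ignores the baseline data. The protocol does not establish that. Section 7 does not name the tested variable; the only natural pairs in this design are baseline and follow-up within a patient, which would use the baseline; and the enrolment-to-conclusion wording for colorimetry also points to change. This stands. It does not remove the point, because change scores gain nothing over follow-up scores at ρ = 0.5, lose at 0.3, and trail ANCOVA even at 0.7.

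A reader might also infer that a chance imbalance is counted in full as treatment effect, or that the test is invalid because of it. Neither is supported: the carry-over is proportional to ρ, and over all randomisations the error rate of an independent-groups rank test stays at its nominal level. Nor does silence on stratification in Section 5.3 show that allocation is unstratified.

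The gain should not be called large without qualification. It depends on a correlation the protocol does not give, is small at 0.3 and absent at 0.2. At d = 1.7 an unadjusted rank test already has ample power.

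Finally, covariates are often left to an analysis plan, and a simple rank comparison of subjective scales is defensible in a feasibility study. That would carry weight had Section 7 been silent. It instead commits to one named test, which cannot take a covariate and does not fit the design, so an analysis plan using ANCOVA would depart from the protocol.

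**Conclusion.** The point holds in this form. Section 7 commits to a paired test that does not fit three independent arms and takes no baseline covariate, while baseline scores are scheduled for every patient. The wrong test is the more basic fault; baseline adjustment is the improvement to make when correcting it.

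The benefit is real from moderate correlation upward: at ρ = 0.5 the detectable difference falls from 1.30 to 1.15 SD, and power at 1.0 SD rises by about 10 percentage points. At 0.3 the rise is about 2 points. These figures assume ρ, full follow-up of 10 per arm, roughly normal scores, equal variances and a common slope. The imbalance argument concerns conditional bias, not overall type I error. For this trial the main value is narrower intervals and usable planning quantities. It should be changed, but it is not a threat to the trial's validity through baseline imbalance.

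**What to change.** Replace the test sentence in Section 7 with the following:

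- For each scale, at each stated follow-up visit, an ANCOVA of the follow-up score on arm (three levels) and that scale's week 0 score. Colorimetry has only the month 8 follow-up.
- Adjusted mean differences with 95% CIs for combined laser versus single laser and combined laser versus control, the comparisons in Section 3.2.
- A rank-based independent-groups analysis of the same contrasts as sensitivity analysis, naming the variable ranked.
- The observed baseline/follow-up correlation and residual SD for each scale, for sizing the main trial.

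The cost is a rewritten sentence and one residual degree of freedom (27 to 26), with no new data or visits. Section 7 also ties all analysis to one software package, so confirm that it fits this model or name another. If the correlation proves to be about 0.2 or lower, adjustment gains nothing and costs at most about 0.03 SD in detectable difference (1.33 against 1.30 SD at zero correlation, as 1.30 × √1.04 = 1.33).

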## 8. Harms

## Definitions

Adverse Event (AE): any untoward medical occurrence in a participant or clinical trial subject whether or not related to any research procedures or to the intervention Non-serious adverse events which are not related to study procedures or to the intervention will not be reported in this study.

Adverse Reaction (AR): an adverse event judged as having a reasonable causal relationship to the intervention or to study procedures will be considered an Adverse Reaction. The existence of a 'reasonable causal relationship' will be judged by the researcher reporting the event. Any evidence or argument to suggest a causal relationship will also be reported.

In this study, adverse reactions will be reported regardless of seriousness.

Serious Adverse Event (SAE) and Serious Adverse Reaction (SAR): any untoward and unexpected medical occurrence or effect that:

- Results in death
- Is life-threatening

- Requires hospitalisation, or prolongation of existing in participants' hospitalisation
- Results in persistent or significant disability or incapacity
- Is a congenital anomaly or birth defect

Medical judgement should be exercised in deciding whether an AE/AR is serious in other situations.

An AE meeting any one of these criteria will be a SAE. An AR meeting any one of these criteria will be a SAR.

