## 1. COMBINED & SINGLE AFCO2 LASER GROUP

In the combination laser group, PDL therapy will always be delivered first using the 595nm VBeam Perfecta (Candela) with the following settings:

10mm spot size (or proportionate to scar size and shape)
0.45 millisecond pulse duration
1.5Hz
5-7 Joule/cm^2 fluence
No overlap
Single pass
Dynamic cooling device 20/30 setting

The energy is selected to produce a degree of purpura/bruising during treatment without skin blanching. The skin response is instantaneous and should be dark purple to black. Whitening in the treatment area suggests over-treatment and is to be avoided. Once the desired response is seen, the entire trial scar is to be treated.

AFCO2L therapy is delivered using the 10,600nm fractional CO2 Ultrapulse laser (Lumenis) with the following settings:

30mJ – 50mJ micropulse energy Rate 300Hz 5% density DeepFX setting No overlap Single pass CLIPSO Feasibility Protocol Version 1.7 8th March 2023; IRAS ID 301064

A cool compress will be applied for 10 minutes following laser completion to dissipate any residual heat. All laser will be administered by the study PI who has laser experience and training.

Following laser delivery, vaseline emollient will be applied topically to all laser sites and dressed with non-adhesive silicone dressing. Patients are advised to remove these at home after 48 hours then apply paraffin emollient twice daily to all treated areas for two weeks. Patients are advised to avoid swimming for two weeks following laser. Following removal of dressings, all sites will be treated with standard scar treatments (pressure garment treatment, silicone, massage and moisturiser) by the scar therapy team.

The laser treatment will be delivered to intervention sites three times at six-week intervals. The time points for intervention have been determined based on a data from previous published research, as well as the clinical expertise of the PI who has conducted laser treatments and clinically evaluated individual response to therapy.

All laser settings will be recorded for each visit. At subsequent visits, participants will be asked to report any adverse effects of the treatment and laser will be delivered using the previous settings.

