## **Reporting procedures**

All related AEs and ARs should be reported to the CI or delegated individual. Depending on the nature of the event, the reporting procedures below should be followed. Any questions concerning adverse event reporting should be directed to the CI in the first instance, or delegated individual in the CIs absence. Severity of the adverse event should be reported along with the potential causality. It should also be documented as to whether it represents an unexpected or anticipated event. SAEs and SARs should be reported within 24 hours of becoming aware of the event.

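### Related-only reporting of non-serious adverse events gives local events at a control scar little route into the report, so laser and control counts of these events would reflect attribution as well as treatment

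*Protocol*

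**What the plan says.** Section 8 (Harms, Definitions) sets the rule for non-serious events: "Non-serious adverse events which are not related to study procedures or to the intervention will not be reported in this study". Those that remain are adverse reactions: "In this study, adverse reactions will be reported regardless of seriousness". The causal judgement is assigned as follows: "The existence of a 'reasonable causal relationship' will be judged by the researcher reporting the event". No blinded or independent review of that judgement is stated.

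Reporting procedures, in the same section, applies the same filter: "All related AEs and ARs should be reported to the CI or delegated individual". Serious events are handled differently and are not limited to related ones: "SAEs and SARs should be reported within 24 hours of becoming aware of the event".

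Active questioning about harm appears once, in the laser-group part of section 5.1: "At subsequent visits, participants will be asked to report any adverse effects of the treatment". The same part says who delivers laser: "All laser will be administered by the study PI who has laser experience and training".

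Section 5.4 gives the laser arms visits 1 to 5 and the control arm visits 1, 4 and 5 only. Section 5.2 states that patients cannot be blinded; only the outcome assessor is.

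**The concern.** A healing burn scar has minor local events of its own, whether or not it is lasered. The randomised control arm is what separates these from harm caused by laser, but only if the same events are counted in the same way in every arm. Here a non-serious event is reported only after someone has linked it to the intervention or a study procedure. A lasered patient has an obvious candidate cause. A control patient has almost none, because the study adds only scales, questionnaires, photographs and colorimetry to usual scar care.

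The bias can run either way. Background events attributed to laser make laser look more harmful than it is. Laser harm put down to the burn makes it look safer.

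What is at stake is the set of local-event counts by arm that the planned multi-centre trial could otherwise take from this study. An analysis plan cannot restore events that the protocol keeps out of the report.

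**Working it through.** **Plan's own figure.** The protocol states no rate, count or sample size for harms. Its one sample-size figure (section 5.6, 7 for Cohen's d 1.7 at 80% power and alpha 0.05) is for efficacy. It reproduces as 6.55, rounded up to 7 per group, with a two-sided two-sample t-test, and has no bearing here. The point rests on the text.

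**Following one event through the rule.** Take the same non-serious infection of the study scar in two patients.

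- *Laser patient.* Asked about treatment effects at visits after laser. If the reporter attributes the infection to laser, it is an adverse reaction and is reported; if not, it is not reported.
- *Control patient.* No laser, no visits 2 and 3, and no stated question about adverse effects. The study procedures are very unlikely causes. Standard scar therapy goes to every arm (section 5.1), and section 7 contrasts control with intervention groups, so the natural reading of intervention is laser. The event has little route to being reported.

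**What is already comparable (sections 5.4, 5.5 and 8).**

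| Domain | Source | Every arm? |
|---|---|---|
| Serious events | 24-hour reporting | Yes |
| Pain, itch | POSAS, BBSIP | Yes: baseline, months 4 and 8 |
| Appearance, colour, texture | MSS, POSAS, photographs | Yes: baseline, months 4 and 8 |
| Redness, pigment | Colorimeter | Yes: baseline, month 8 |
| Infection, blistering, skin breakdown | Adverse-event reporting only | No: filtered by attribution |

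The gap is the last row.

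**Illustration on assumed rates.** Inputs from section 5.6: 10 per arm, so 20 laser and 10 control. Assumed: a true proportion p with such an event, equal in all arms, of 20%, 40% or 60%; a probability of attribution of 0.5 to 0.8 on laser (aL) and 0 to 0.05 on control (aC).

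Expected reported = n × p × a.

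| p | True laser (20p) | True control (10p) | Reported laser | Reported control |
|---|---|---|---|---|
| 20% | 4 | 2 | 2.0-3.2 | 0-0.1 |
| 40% | 8 | 4 | 4.0-6.4 | 0-0.2 |
| 60% | 12 | 6 | 6.0-9.6 | 0-0.3 |

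Reported difference in proportions = pL × aL − pC × aC.

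- No true difference, pL = pC = 40%, aL = 0.5, aC = 0.05: 20% − 2% = 18 percentage points, against a true value of 0.
- True difference of 40 points, pL = 60%, pC = 20%, same attribution: 30% − 1% = 29 points, an understatement of 11.
- Extreme case, equal true rates of 40%, every laser event attributed and no control event: 8 of 20 against 0 of 10, Fisher two-sided p = 0.029, with no true difference.

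These figures show direction and possible size. They are not estimates for this trial.

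**The case against.** The strongest reply is that related-only reporting is a deliberate and consistent choice for lasers in routine use at the host institution, and that it defeats no stated objective. The objectives in section 3.2 concern appearance, itch and psychological sequelae. Section 7 plans no harms comparison, and the trial summary in section 1 says the study informs the larger trial on power, measurement frequency and treatment streams, not harm rates. Even complete capture would be imprecise: 1 of 10 against 4 of 10 gives a Fisher two-sided p of about 0.30. All of this stands, and it sets the priority. It does not make the counts comparable if anyone tabulates them by arm.

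Four stronger readings are tempting, and the documents do not support them.

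- *Unrelated events are never captured.* The text says they are not reported; it does not say they are not recorded. Section 5.5 draws scar-management interventions from the medical record without restriction by arm. Still, no section sets up systematic capture regardless of cause.
- *The control count is zero by definition.* Section 5.1, headed Intervention, also covers standard scar therapy, so on a broad reading a reaction to a garment or silicone in a control patient could count as related. Few is a fair inference; none is not.
- *Laser and standard care cannot be compared on harm at all.* Serious events, pain, itch, pigment and appearance are collected in every arm.
- *The person delivering laser judges causality.* The protocol says only that it "will be judged by the researcher reporting the event". That may be the PI, but this is not stated.

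**Conclusion.** The point holds in a limited form. As written, the rule makes laser and control counts of non-serious local events depend on attribution as well as treatment, and the direction of the resulting bias cannot be known in advance. It affects events such as infection, blistering and skin breakdown that the scheduled scales and colorimetry do not capture.

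The conclusion rests on reading intervention as laser, which the use of the word in section 7 supports, and on there being no other provision for collecting these events whatever their cause; the protocol contains none. The size is unknown because the protocol gives no rates. On the assumed values, a spurious difference of the order of 18 percentage points is possible with equal true rates.

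Because harms comparison is not a listed objective and each arm has 10 patients, this is a modest-priority improvement and does not threaten the efficacy comparison.

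**What to change.** In section 8, require that non-serious events at the study scar be recorded and reported in all three arms whatever the causality judgement. Keep the relatedness filter for events remote from the scar. Hold causality as a separate field, completed after the event is recorded, and tabulate study-scar events by randomised arm before any causality filter.

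Two details are needed for the change to work.

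- *Equal ascertainment.* Controls have no visits 2 and 3, so ask the same questions over the same recall windows at months 4 and 8 in every arm, and base the between-arm table on those answers. List events elicited at the laser-only visits 2 and 3 separately.
- *Protecting the blind.* Have the questions asked by a team member other than the blinded outcome assessor, since answers about blistering or wounds could reveal the arm.

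The cost is protocol wording, a short form at existing visits and slightly more event data for 30 patients, with no extra visits or change in treatment. Participants still know their arm, and laser patients will have been asked in between, so some reporting difference may remain. The change removes the attribution filter, not every source of bias.

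### The SAE/SAR definition contradicts itself on whether an event must be unexpected to be serious, so it is unclear whether anticipated serious events fall under the 24-hour report

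*Protocol*

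**What the plan says.** Protocol section 8 (Harms, Definitions) first defines an adverse event as "any untoward medical occurrence in a participant or clinical trial subject whether or not related to any research procedures or to the intervention". Expectedness plays no part in that definition, nor in the definition of an adverse reaction, which turns on a reasonable causal relationship.

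Serious adverse events (SAEs) and serious adverse reactions (SARs) are then defined together as "any untoward and unexpected medical occurrence or effect that" leads to one of five outcomes: death, threat to life, new or prolonged hospital stay, lasting or significant disability, or congenital anomaly. The definition closes with two further sentences: "An AE meeting any one of these criteria will be a SAE", and "An AR meeting any one of these criteria will be a SAR".

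Two sentences in the same section settle what is reported at all: "Non-serious adverse events which are not related to study procedures or to the intervention will not be reported in this study", and "In this study, adverse reactions will be reported regardless of seriousness".

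Reporting procedures asks for related events to go to the chief investigator or a delegate, with severity and causality. On expectedness it says: "It should also be documented as to whether it represents an unexpected or anticipated event". On timing it says: "SAEs and SARs should be reported within 24 hours of becoming aware of the event".

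**The concern.** Seriousness describes what an event led to. Expectedness describes whether it was foreseen. The lead-in to the SAE/SAR definition joins the two, so that a foreseen event could fail the definition whatever its outcome. The rest of the section keeps them apart.

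This matters because two reporting rules depend on the serious label. The 24-hour limit applies to SAEs and SARs only. For an event judged unrelated to the study, the label is also the only route to any report, because unrelated non-serious events are left out by design. If a foreseen event can lose the label, it can lose the time limit and, when unrelated, the report itself.

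Some sorting into anticipated and unanticipated will take place in this trial. Section 5.2 describes effects that laser treatment is known to produce, section 6 requires known side effects to be explained to participants, and Reporting procedures asks for the classification. Section 8 names no reference for making it, so under the lead-in one reporter's judgement of what was foreseeable could decide whether an event counts as serious. The study is meant to inform a larger multi-centre trial (sections 1 and 4.1), and ambiguous wording carried forward would be applied by more reporters.

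**Working it through.** There is no figure to reproduce. The check sets the sentences of section 8 side by side and follows one type of event through them: an event that was anticipated and that meets one of the five outcomes.

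**Step 1. Is it an SAE or SAR?**

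- Lead-in ("any untoward and unexpected medical occurrence or effect that"): no, because it was not unexpected.
- Closing sentences ("An AE meeting any one of these criteria will be a SAE" and the matching SAR sentence): yes. The criteria they refer to are the five listed outcomes, and neither the adverse event nor the adverse reaction definition asks for unexpectedness.

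The two readings give opposite answers.

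**Step 2. Does Reporting procedures favour one reading?** It does. It asks for each reported event to be marked as unexpected or anticipated. If every SAE and SAR were unexpected by definition, that mark would be the same for all of them and would tell the reader nothing about serious events. The instruction fits the closing sentences better than the lead-in. It is indirect evidence only, since the mark would still be informative for non-serious reactions.

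**Step 3. What follows for reporting?**

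| Anticipated event meeting a listed outcome | Following the lead-in | Following the closing sentences |
|---|---|---|
| Related to intervention or study procedures | Not a SAR. Still reported, since all adverse reactions are, but without the serious label or a stated time limit | SAR, due within 24 hours |
| Unrelated | Not an SAE. Can be handled as non-serious and unrelated, and so not reported | SAE, due within 24 hours |

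For an unexpected event with the same outcome the two readings agree: it is serious and due within 24 hours. The conflict is confined to anticipated events.

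**Step 4. Does another sentence close the gap?** Section 8 also allows medical judgement on seriousness, but for situations beyond the listed criteria and at the reporter's discretion. It does not say which reading governs an anticipated event that meets a listed criterion.

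**Step 5. Can the loss be sized?** No. It would need the rate of serious events, the share that reporters class as anticipated, and the share of reporters who apply the lead-in over the closing sentences. The Protocol gives none of these.

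**The case against.** The strongest reply is that the closing sentences are the working rule. They are stated without qualification, they come last, and they bring every anticipated serious event back in. Reporting procedures points the same way, and the study commits itself to GCP. On that view the lead-in is a slip of wording that a careful reporter would not act on. This part of the reply stands: most of section 8 favours reporting, and it cannot be said that anticipated serious events *do* fall outside the definition. What remains is that nothing says which sentence prevails, and the lead-in is the sentence presented as the definition.

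A second reply is that treatment harms are not lost. This also stands. Adverse reactions are reported whatever their seriousness, so a related anticipated serious event is reported under either reading and risks only its label and its deadline. A reader might infer that the harms summary carried to the main trial would be too low. The Protocol does not support that: only unrelated anticipated serious events could go unreported, and only if the reporter follows the lead-in.

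A third reply is that the effects the Protocol itself anticipates in section 5.2 (heat, discomfort, bruising, temporary laser channels) meet none of the five outcomes, so the document names no event that is both anticipated and serious. That is fair, and it limits the practical stakes. It does not settle the unrelated events, which need not be effects of the laser at all.

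A reader might also try to size the problem by laser exposures, 20 laser-arm participants × 3 sessions = 60. That is the wrong denominator. The events that could go unreported are unrelated ones, which do not depend on laser sessions and can arise in all 30 participants, including the 10 controls.

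**Conclusion.** The point holds as an internal contradiction. The lead-in of the SAE/SAR definition makes unexpectedness a condition of seriousness. The closing sentences of the same definition do not, and Reporting procedures treats expectedness as a separate attribute. As a result the Protocol leaves it unclear whether an anticipated serious event is due within 24 hours.

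The consequence has two parts, both conditional on a reporter following the lead-in. A related anticipated serious event could lose the serious label and the 24-hour limit while still being reported as an adverse reaction. An unrelated anticipated serious event could go unreported. No number can be attached to either. The conclusion rests only on the wording of section 8 and assumes nothing about event rates. The correction is worth making because the lead-in, taken literally, gives a wrong result for a safety-reporting rule, and because it is so easily put right.

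**What to change.** In Protocol section 8, Definitions, delete *and unexpected* from the lead-in to the SAE/SAR definition. It then matches the adverse event definition and its own closing sentences. Leave the instruction in Reporting procedures to record each event as unexpected or anticipated, so that no information on expectedness is lost.

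The cost is two deleted words, made under the Protocol's own amendment procedure. The only downside is at most a few additional 24-hour reports, for anticipated serious events that some reporters would otherwise have left out. With no event rate in the document, that number cannot be given more exactly.
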